3.2. SCHEDULE OF EVENTS

Schedule of events can be found in Appendix 1 of the protocol.

3.3. CHANGES TO ANALYSIS FROM PROTOCOL

- Not applicable.

4. PLANNED ANALYSES

The following analyses will be performed for this study:

- Main Analysis
- Final Analysis

4.1. MAIN ANALYSIS

A Main Analysis will take place for this study at the end of the Double-Blind Treatment Period when all subjects have completed Week 24 visit or discontinued from the study prior to Week 24. The results of which will be based on the unblinded treatment groups. All planned Main Study Analyses identified in this SAP will be performed by IQVIA Biostatistics following Pfizer Pharmaceutical Sponsor Authorization of this SAP, database unblinding, and Analysis Sets.

Derivations and definitions for the Main Analysis will be based on those required for the final analysis contained in this SAP, unless deviations are stated within the text. The list of outputs provided with the full set of output templates (planned for the final analysis) will highlight which of these outputs will also be provided for the Main Analysis.

After all subjects have completed the Double-Blind Treatment Period or discontinued from the study prior to Week 24, outstanding data queries have been resolved/closed, and the data have been cleaned and finalized, the sponsor will authorize breaking of the study blind for Double Blind Treatment Period and the Main Analysis of the data will be performed. No treatment assignment unblinded, or analyses completed until this SAP has been approved.

At the time of the main analysis, the sponsor staff will be unblinded to the initial treatment assignments at the beginning of Double-Blind Treatment Period, but participants, investigators and site staff will remain blinded. During the Extension Treatment Period, participants, investigators, and site staff will be aware that active treatment is being provided; however, they will remain blinded to the dose assignments. An unblinded team at IQVIA will receive the Double-Blind Treatment assignments and perform the Main Analysis

4.2. FINAL ANALYSIS

The Final Analysis will occur when all subjects have completed the Extension Treatment Period or discontinued from the study. All final, planned analyses identified in SAP will be performed by IQVIA Biostatistics following Pfizer Sponsor Authorization of this SAP, database unblinding, and Analysis Sets.

After all subjects have completed the study, outstanding data queries have been resolved/closed, and the data have been cleaned and finalized, the sponsor will authorize locking the database, unblinding for the second randomization schedule used for subjects receiving placebo in the Double Blind Treatment period and entering into the extension period and the final analysis of the data will be performed. No database may be unblinded or analyses completed until this SAP has been approved.

Any, post-hoc, CCI [REDACTED] completed to support planned study analyses, which were not identified in this SAP, will be documented and reported in the clinical study report. Any results from these unplanned analyses will also be clearly identified in the text of the clinical study report. CCI [REDACTED]
[REDACTED]

Unless specified otherwise, the following treatment (treatment sequence) will be used for Double-blind Treatment Period and Extension Treatment Period, respectively:

List of treatments/treatment sequences

Study Period	Treatment / Treatment Sequence
Double-Blind Treatment Period	
 • etrasimod 1 mg • etrasimod 2mg • etrasimod any dose • Placebo
Extension Treatment Period	
 • etrasimod 1 mg – 1 mg • etrasimod 2mg – 2 mg • Placebo – etrasimod 1 mg • Placebo – etrasimod 2 mg

5. ANALYSIS SETS

Agreement and authorization of subjects included/excluded from each analysis set will be conducted prior to the unblinding of the study for the Main Analysis and Final Analysis.

5.1. PROCESS FOR ANALYSIS SET ASSIGNMENT

Before the database is unblinding for the Main Analysis and Final Analysis, the subjects excluded from each analysis set and the reason for exclusion will be sent to Pfizer for blinded review. The Clinical Protocol Deviation log file will be needed to define the Per Protocol Set for each analysis. This file will be incorporated into the analysis datasets and used, along with programmable deviations, to determine which subjects to include in the Per Protocol Set. Any changes to the analysis sets will occur before the database is unblinded. Pfizer will approve the final analysis sets which will be used for analyses prior to database unblinding. Once the analysis sets are approved, the subjects will be unblinded. Any additional analysis set assignments after database unblinding will also need to be approved.

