10.5. Pharmacokinetic Assessments

Blood samples for plasma analysis of etrasimod will be collected at the following timepoints from all subjects who received ≥ 1 dose of study drug (etrasimod or placebo):

- Predose and at 4 hours (± 15 minutes) postdose (after ECG) on Day 1
- Predose (trough; within 60 minutes prior to dosing) at Weeks 4, 8, 16, 24, 28, 32, 46, and 52 or at the ET Visit, if applicable

- At the 4-Week Safety Follow-Up Visit (28 days [\pm 3 days] after the last dose of study drug)
- If possible, at the time of an AE leading to study drug discontinuation or when there is a significant AE such as a severe or atypical infection (including but not limited to systemic infections like sepsis) and severe drug induced liver injury that meets Hy's criteria [49]. The time of the last study treatment dose should be documented.

Subjects should be instructed to document the time of their last dose prior to the study visit (Section 7.4) and the time must be recorded in the eCRF. The time of PK sample obtained pre-dose and when study drug is administered during the study visit must also be recorded in the source.

Blood samples will be processed for collection of plasma fractions for determination of the concentrations of etrasimod and, if warranted, metabolites of interest. Blood samples collected for PK analyses may also be used for profiling of drug-binding proteins, bioanalytical method validation purposes, stability assessments, metabolite assessments, or to assess other actions of etrasimod with plasma constituents.

No urine samples will be collected for PK analysis.

Drug concentration information that would unblind the study will not be reported to investigative sites or blinded personnel until the study has been unblinded.

Planned timepoints for all PK assessments are provided in the Schedules of Assessments (Appendix 1; Table 7 and Table 8).

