11.3. Analysis Sets

For purposes of analysis, the following analysis sets are defined for each treatment period as shown in [Table 6](#).

Table 6: Analysis Sets

Analysis Set	Description
Full Analysis Set (FAS); (Double-Blind Treatment Period)	The FAS will include all randomized subjects in the Double-Blind Treatment Period, who receive at least 1 dose of study treatment. Subjects will be summarized by treatment to which they were randomized, regardless of treatment actually received.
Modified Full Analysis Set (mFAS); (Double-Blind Treatment Period)	The mFAS will include all randomized subjects who receive at least one dose of study medication and have a baseline measurement and have at least 1 post-randomization measurement. The mFAS is endpoint specific, therefore subjects included in the analysis set for one endpoint may differ from another endpoint, based on the baseline and post-baseline data.
Per Protocol Set; (Double-Blind Treatment Period)	The Per Protocol will include all subjects from the FAS without major protocol violations that might affect the evaluation of the effect of study treatment on the primary endpoint. The Per Protocol will be used in sensitivity analyses of the primary and secondary endpoints to evaluate the influence of major protocol violators and protocol deviators on the main efficacy results. Subjects may be excluded from this population if they violate the eligibility criteria or significantly deviate from the study plan. Specific reasons for warranting exclusion from this population will be documented prior to database lock and may include, but are not limited to, study treatment noncompliance, receiving incorrect study treatment, and missing more than a defined number of visits while still on study. The statistical analysis plan, which will be finalized prior to database lock, will be the final documentation for the Per Protocol Set definition.
Pharmacokinetic Set; (Double-Blind Treatment Period)	The Pharmacokinetic Set will include all subjects in the FAS with at least 1 postdose PK measurement.
Safety Set; (Double Blind Treatment Period and Extension Treatment Period)	The Safety Set will include all randomized subjects who received at least one dose of study treatment during the specified treatment period.

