5.8. PHARMACOKINETIC SET

The Pharmacokinetic Set will include all subjects in the Safety Set with at least 1 quantifiable postdose PK measurement of etrasimod which is not impacted by protocol violations or events with potential to affect the PK concentration.

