17.1.2. MISSING DATA METHODS FOR PRIMARY EFFICACY VARIABLE

Subjects who 1) discontinue the study for worsening of disease, lack of efficacy, or adverse event related to EoE, 2) use a rescue medication for EoE, or 3) have rescue medical procedure during the study as confirmed after blinded review by clinical and medical team members before study unblinding will be considered to have a missing outcome in the analysis of all efficacy endpoints at any subsequent timepoints, including the primary endpoint. The rescue medications/rescue medical procedure will be identified by the Pfizer clinical team during blinded data review. The detailed information regarding the identification of rescue therapy is provided in Appendix 4. In scenarios 2 and 3 above, if a subject has an efficacy measurement collected after the initiation of rescue medication/rescue medical procedure, the observed data will be censored at the time of initiation and they will be considered as having a missing outcome. Subjects in all 3 scenarios above may still be included in the respective Per Protocol Set, provided they do not violate other criteria for Per Protocol Set. For example, they will be excluded from the respective Per Protocol Set if they initiate a prohibited medication before the Week 16 efficacy assessment that can affect efficacy of the study treatment and the indication is unrelated to EoE.

Analysis visits will be mapped as per Section 6.4 before any missing data imputation method is applied.

Subjects who initiate rescue medication will have PEC results after the start of rescue medication/rescue medical procedure set to missing. All missing PEC at Week 16 and Week 24 will then be imputed using multiple imputation under missing at random (MAR) procedure with a fully conditional specification (FCS) and predictive mean

matching for PEC as the primary missing data method. There are two different types of missing data patterns: non-monotone and monotone. A subject with missing data at any post-Baseline visit, and a non-missing data point after that visit is said to have intermittent missing data (non-monotone). A subject with missing data at any post-Baseline visit and at all subsequent visits is said to have monotone missing data.

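### The pre-unblinding review of analysis-set exclusions does not exempt the Pharmacokinetic Set, and the list for that set would largely show who is on placebo

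*SAP*

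**What the plan says.** **Review before unblinding.** SAP 5 states: "Agreement and authorization of subjects included/excluded from each analysis set will be conducted prior to the unblinding of the study". SAP 5.1 gives the mechanics: "the subjects excluded from each analysis set and the reason for exclusion will be sent to Pfizer for blinded review", and then "Pfizer will approve the final analysis sets which will be used for analyses prior to database unblinding". Both sections cover every set and name no firewalled recipient. The last sentence of SAP 5.1 does allow for further set assignments after unblinding, subject to approval.

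**Two definitions of the Pharmacokinetic Set.** Protocol 11.3, Table 6: "The Pharmacokinetic Set will include all subjects in the FAS with at least 1 postdose PK measurement". The table labels this set as belonging to the Double-Blind Treatment Period. SAP 5.8 instead takes "all subjects in the Safety Set with at least 1 quantifiable postdose PK measurement of etrasimod", adds a condition about protocol violations and similar events, and names no period. SAP 3.3 reports no changes to the analysis from the protocol.

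**Blinding rules.** Protocol 6.5 keeps the sponsor blinded until the Week 24 dose selection analysis. Protocol 10.5 adds: "Drug concentration information that would unblind the study will not be reported to investigative sites or blinded personnel until the study has been unblinded".

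**Other judgements in the sponsor's blinded review.** Under SAP 5.1 and 5.5, Per Protocol membership is settled in the same review, partly by judging whether a deviation is serious enough. SAP 17.1.2 says: "The rescue medications/rescue medical procedure will be identified by the Pfizer clinical team during blinded data review".

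**The concern.** A list of who is in or out of an analysis set is normally safe to review blind, because membership does not depend on treatment. The Pharmacokinetic Set as SAP 5.8 defines it is different: membership depends on drug being found in the blood. Absence from the set, with the stated reason that no etrasimod was quantifiable, amounts to a treatment assignment.

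At stake is the blinding of decisions that the sponsor still has to make when it receives the list. The clearest case is the Per Protocol Set, because its exclusions travel in the same submission and involve discretion. Rescue determinations are a possible second case if any are still open. They set later PEC values to missing, and SAP Appendix 4 lets reviewers class some other treatments as rescue when they judge the effect on efficacy assessment to be significant.

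**Working it through.** The plan states no figure on this point, so there is none to reproduce. The check is a reading of the passages together, followed by a simple probability.

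**Step 1. Does the set separate the arms?** Protocol 10.5 takes PK samples from all dosed subjects, placebo included, with a first postdose sample 4 hours after the Day 1 dose. Nearly every dosed etrasimod subject should therefore have a postdose sample. A correctly dosed placebo subject can have no quantifiable etrasimod in the double-blind period and so fails SAP 5.8. The wording in Table 6, which asks only for a measurement, does not by itself exclude every placebo subject.

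**Step 2. Can the passages all be followed?** If SAP 5.1 is followed for this set, blinded sponsor staff receive concentration information that reveals treatment, contrary to Protocol 10.5 and 6.5. If Protocol 10.5 is followed, the set cannot be reviewed and approved by blinded staff before unblinding, as SAP 5 and 5.1 require. The passages need reconciling either way.

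**Step 3. How informative is the list?** Inputs: 96 planned subjects, allocated 3:3:2 (protocol synopsis).

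- Expected placebo: 96 × 2/8 = 24. Expected active: 96 − 24 = 72. Prior probability of placebo: 24/96 = 25%.
- Let f be the share of active subjects excluded (missing samples, or samples affected by deviations).
- Let g be the share of placebo subjects who do have a quantifiable result, which is possible only if extension samples count.
- The documents give neither f nor g, so both are assumptions.

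P(placebo | listed) = 24(1 − g) / [24(1 − g) + 72f]

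| | Placebo listed | f = 0 | f = 2% | f = 5% | f = 10% |
|---|---|---|---|---|---|
| g = 0 | 24 | 100% | 94% | 87% | 77% |
| g = 50% | 12 | 100% | 89% | 77% | 63% |
| g = 80% | 4.8 | 100% | 77% | 57% | 40% |

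Example (g = 0, f = 10%): 24 / (24 + 7.2) = 77%.

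With g = 0, everyone not listed is on active drug. With g = 50%, P(placebo | not listed) is 14-16%, and with g = 80% it is 21-23%.

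These figures ignore the reason column. That column would largely separate subjects with no quantifiable level from those excluded for a deviation, so the list as sent would tell the reader more than the table shows.

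**Step 4. Which row applies?** The double-blind label in Table 6 gives g = 0. SAP 5.8 does not repeat that limit. The Main Analysis waits until every subject has completed Week 24 or discontinued (SAP 4.1), and extension PK sampling starts at Week 28. Placebo subjects enrolled early could therefore have quantifiable extension samples by then, and g could exceed 0.

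**Step 5. Which analysis?** Only the Main Analysis is affected. By the Final Analysis the sponsor already knows the initial assignments (SAP 4.1), and membership of this set does not show whether a former placebo subject was re-randomized to 1 mg or 2 mg.

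**The case against.** The strongest reply is that controls already exist. The SAP is based on a protocol whose section 10.5 withholds such concentrations from blinded personnel, and SAP 5.1 itself calls the step a blinded review. Its last sentence gives a route for assigning a set after unblinding. A careful team would simply leave the Pharmacokinetic Set off the list. This is fair as a prediction of conduct, and nothing here shows that a leak occurred. It does not remove the textual conflict, because SAP 5 and 5.1 cover each set and exempt none.

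A reader might infer that the review protecting the primary endpoint is itself unblinded, through the rescue list. The documents do not support that. No passage places rescue identification after receipt of this list. SAP 5.5 makes rescue use a ground for Per Protocol exclusion, and Appendix 4 gives that as one purpose of identifying rescue, so rescue is probably settled before the exclusions are sent (SAP 17.1.2 is less clear-cut on this link). SAP 5.1 names only the company, while SAP 17.1.2 and Appendix 4 name the clinical team and medical reviewers; nothing says that these are the same people. The primary analysis uses the FAS, where membership needs only randomization and one dose and leaves no discretion. The Per Protocol analysis is supplementary.

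A reader might also infer that all 24 placebo subjects are certain to be listed. That depends on the double-blind limit in Table 6. The condition in SAP 5.8, "at least 1 quantifiable postdose PK measurement of etrasimod which is not impacted by protocol violations", can also put active subjects on the list. Both limits are carried in the ranges above.

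**Conclusion.** The point holds as a conflict in the written procedure. Followed literally, SAP 5 and 5.1 together with 5.8 give the sponsor, before the Main Analysis unblinding, a list that largely identifies placebo subjects, contrary to Protocol 10.5 and 6.5.

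On the double-blind reading, about 24 of 96 subjects are listed for lack of quantifiable drug. The probability that a listed subject is on placebo is then about 77-100%, against 25% beforehand, if 0-10% of active subjects are also excluded. If extension samples count, fewer placebo subjects are exposed: about 12 if half of them have a quantifiable level, about 5 if 80% do.

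The blinding of the Per Protocol judgements approved in the same step is at risk, and so is that of any rescue determination not yet final. A general claim that the primary endpoint's review is not blind goes further than the documents allow. The point merits correction because the repair is nearly free.

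**What to change.** In SAP 5 and 5.1, exempt the Pharmacokinetic Set from the list and the approval that precede unblinding. State that the unblinded IQVIA team (SAP 4.1) and the pharmacokineticist assign its membership and exclusion reasons, and that these are released to the sponsor only after the Main Analysis unblinding, under the provision at the end of SAP 5.1. Add a cross-reference to Protocol 10.5. Any input from the sponsor's study physician on affected PK data (SAP 19) that bears on membership should follow the same timing.

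Applying the protocol's definition of the set before unblinding would not be a safe substitute. Table 6 asks for a measurement, and the protocol synopsis says that some placebo samples from the double-blind period will not be assayed. If an unassayed sample is not a measurement, that version of the list could also point to placebo subjects.

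The cost is one or two sentences in the SAP. Data collection and the planned analyses are unchanged, and the unblinded team already exists.

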5.2. SCREENED SET

The Screened Set will contain all subjects who provide informed consent for this study.

5.3. RANDOMIZED SET

The Randomized Set will contain all subjects who are randomized to study treatment.

5.4. FULL ANALYSIS SET

The Full Analysis Set (FAS) will consist of all randomized subjects in the Double-Blind Treatment Period who receive at least 1 dose of study treatment. Subjects will be summarized by treatment to which they were randomized, regardless of treatment actually received.

5.5. PER PROTOCOL SET

The Per Protocol Set will consist of all subjects in the FAS without major protocol violations on or before Week 16 that might affect the evaluation of the effect of study treatment on the primary endpoint. This set will be used in sensitivity analyses of the primary and secondary endpoints to evaluate the influences of major protocol violators and deviators on the primary results. Subjects will be excluded from the Per Protocol Set if they violate the eligibility criteria or significantly deviate from the study plan, including:

- Study treatment non-compliance (< 80 or > 120%)
- Received incorrect study treatment for > 7 days in total
- Used rescue medication or undergo rescue medical procedure that may affect primary efficacy endpoint at Week 16
- Missed Week 16 esophageal PEC in pre-specified analysis window per Section 6.4 for reasons other than discontinuing due to lack of efficacy

All protocol deviations will be reviewed in addition to the programmable deviations listed above (e.g., study treatment non-compliance) to determine if any deviation is significant enough to exclude a subject from the Per Protocol Set. All exclusion flags will be finalized before study unblinding. Subjects excluded from the Per Protocol Set will be listed along with the reason category above. Subjects will be summarized by treatment to which they were randomized, regardless of treatment actually received.

5.6. MODIFIED FULL ANALYSIS SET

The modified FAS (mFAS) will consist of all randomized subjects who receive at least 1 dose of study treatment in the Double-Blind Treatment Period and have a Baseline and at least 1 post-randomization measurement. In addition, subjects with baseline DSQ total score <8 will be excluded from mFAS for DSQ based endpoint analyses. Subjects will be summarized by treatment to which they were randomized, regardless of treatment actually received. Note that the mFAS can vary with endpoints since some subjects may have the needed data for inclusion in the mFAS for some endpoints, but not for other endpoints.

5.7. SAFETY SET

The Safety Set will be derived for both the Double-Blind Treatment Period and the Extension Treatment Period, respectively and includes all randomized subjects who receive at least 1 dose of study treatment during the specified treatment period. In Double-Blind Treatment Period, subjects will be analyzed according to treatment received. In Extension Treatment Period, subjects will be analyzed according to the treatment sequence received, regardless of randomization. The Safety Set will be used for all safety analyses.

